Several studies have shown a reduction of the sympathetic activity measured by microneurography (MSNA) after an exercise training program in heart failure [19, 20]. This is also found on other ANS parameters such as the Heart Rate Variability that is improving [6, 9]. Catecholamines also tends to decrease with aerobic activity [21]. This improvement in vegetative balance is associated with an improvement in the different vegetative reflexes involved in the regulation of cardiovascular ANS. Thus, the abnormalities noted on the baroreflex, the chemoreflex, the ergoreflex and the central control are all potentially improved by repeated aerobic exercise [22, 23]. Thus the sympathetic stimulation induced during the exercise is followed by a period of increase in vagal tone, explaining the benefit on the rhythmic profil . To our knowledge there is no study comparing the effects on the ANS of MICE training versus HIIT training in CHF.

Hypothesis

Our team recently used an intermittent exercise protocol that has been optimized in CHF patients [24] in order to induce a strong cardiovascular and muscular stimulus while ensuring safety and comfort of the patient (30 seconds at 100% of peak power alternate with 30 sec of passive recovery). In 18 CHF patients, we showed that a single intermittent exercise session increases parasympathetic tone (high frequency index in normalized units HFnu%) and significantly decreases premature ventricular contraction within the 24h of the exercise, compared to a single session of MICE [16]. These results appear promising and suggest that stimuli associated with intense intermittent exercise and passive recovery, as opposed to continuous-type exercise of moderate intensity, would be more effective to increase sympatho-vagal balance and arrhythmias. Nevertheless, the effects of a several weeks of an HIIT program on explanatory parameters of sudden death (SNA activity, arrhythmias, cardiac function) have never been studied in CHF patients. We therefore hypothesize that HIIT is superior to MICE for 1/ increasing parasympathetic activity measured by HRV, 2 / the cardiorespiratory fitness. In addition, we also hypothesize that there is a link between improved physical capacity and vagal tone and decreased arrhythmias.

Objectives

Main objective:

To compare, in patients with chronic heart failure, the efficacy of 4-weeks exercise training programs (MICE vs HIIT) on the evolution of the spectral high frequency (HF) component of HRV.

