Secondary Objectives:

To compare, in patients with heart failure, the effectiveness of 4-weeks exercise training programs (MICE vs HIIT) on:

- The temporal and spectral component of HRV
- The number and nature of arrhythmias
- Diastolic and systolic functions measured by echocardiography
- The maximum oxygen consumption (VO₂max)
- Arterial vasomotricity
- biomarkers measurements (BNP, catecholamines)

Routine medical examination

All the evaluations of this research are part of the patient follow-up classically performed in a cardiovascular rehabilitation center. Thus, for this study, the current care evaluated will include: an ECG-24h holter, a maximal cardiopulmonary exercise test, an echocardiography, a blood sample test, an endothelial function analysis (Endopath system). The exams will be done at the inclusion (J0), after 4 weeks of rehabilitation (S4).

Cardiopulmonary Exercise Test

CPET will be performed according to current guidelines for CHF patients [12]. A continuous progressive exercise protocol will be performed on a cycle ergometer (Ergoline 800S, Ergoline, Bitz, Germany). A 2-min warm-up at 20 W ; and the power will be increased by 10 W/min until exhaustion [12]. Peak power output (PPO) is define as the power output reached at the last fully completed stage. All subjects will be encouraged to provide a maximal effort. Oxygen ($\dot{V}O_2$) and carbon dioxide (CO_2) were registered by a breath by breath analysis (PowerCube, Ganshorn Electronic Medizin, Germany). Heart rate, blood pressure, and rating of perceived exertion (RPE) using the Borg scale (level 6 to 20) will be recorded before the test and at 2-min intervals during exercise and recovery. Electrocardiographic activity will be continuously monitored using a 12-lead ECG (GE Healthcare Marquette) and will be recorded throughout the test and during the 6-min passive recovery after the test.

24-h Holter ECG recording

24-h ECG monitoring will be performed at baseline and at the end of the stay using a two-lead 24-h Holter ECG system (Spiderview, ELA medical, France). Patients will be requested to avoid any exercise, caffeinated beverages, and smoking during the 24 h of recording. An experienced technician blinded to randomization will analyse the recordings (Synescope, ELA medical, France).

Echocardiography

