Adrenaline, norepinephrine (ng.L)

NT pro BNP (ng.L)

Design of the study

Prospective / randomized study in 2 parallel groups (1:1): arm 1 (MICE) and arm 2 (HIIT).

Randomization

The randomization to assign each patient to one of the 2 groups will be done just after the verification of the eligibility criteria and the collection of the sign consent of participation of the patient. The numbers of the 2 groups (arm 1: MICE / arm 2: HIIT) are balanced with a 1: 1 ratio

Eligibility criteria (inclusion / exclusion)

Inclusion

Inclusion criteria will be stable CHF with NYHA functional class from I to III, stable left ventricular ejection fraction (LVEF) < 45% over at least 6 months, stable optimal medical therapy including a beta-blocker and an angiotensin-converting enzyme (ACE) inhibitor or angiotensin receptor blockers (ARB) for at least 6 weeks and ability to perform a maximal CPET.

Exclusion

Exclusion criteria will be any relative or absolute contraindications to exercise training according to current recommendations [12], fixed-rate pacemaker with HR limits set lower than exercise training target HR, major cardiovascular event or procedure within the 3 months preceding enrolment, chronic atrial fibrillation, heart failure secondary to significant uncorrected primary valve disease (except for mitral regurgitation secondary to left ventricular dysfunction), and heart failure secondary to congenital heart disease or obstructive cardiomyopathy.

Patients eligible for the study must not have participated in biomedical research within 30 days of the start of this research and will not be able to participate in another research at the same time.

Recruitment

The recruitment of CHF patients will be done only at the Clinic of Saint-Orens, during the first day of consultation and only by investigators avowed by the Ethical Committee. After verification of the eligibility criteria, the cardiologist will explain to the patient the research and propose to participate. He will then give him the information notice. The expected duration of the inclusion period is 1 year.

Expected fallout

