If HIIT is more interesting to improve ANS activity, arrhythmias, cardiac function and cardiorespiratory fitness (all are parameters of sudden cardiac death), then the optimization and the prescription of this type of exercise training would be important. That would demonstrate the great interest and the feasibility of an intense exercise training program specific to chronic heart failure patients. This prescription could later be transposable at home for a long term period of practice. Thus this study will open the field to other research perspectives in particular in terms of longer-term impact on the mortality that remains to be evaluated.

Statistics

Sample Size

The primary outcome measure is the change of High Frequency power in normalized units (HFnu) measure at night as a surrogate of cardiac parasympathetic modulation. Based on our first study [16], we hypothesise that HIIT mode will induce a ~11% change in HFnu compare to MICT training mode. With a mean value of the main criteria (HFnu %) of 31.5%, a standard deviation of 3%, a statistical power (1- β) to 90% and a α risk set to 0.05 in bilateral hypothesis, 16 patient per group must be recruited.

Statistical analyses

Data will be summarized by mean \pm standard deviation (SD) for continuous variables; percentages and frequencies for categorical ones. Shapiro-Wilk and Bartlett tests will be used to assess normality and equality of variance among variables analysed, respectively. Baseline inclusion characteristics will be compared between groups using one-way ANOVA or Mann-Whitney non-parametric test for quantitative variables. Changes within groups (difference between post and pre training values) will be analysed using a paired t-test for normally distributed data or paired Wilcoxon signed-rank test for non-normally distributed data. To analyse the differences between HIIT and MICT groups, repeated ANOVA analysis will be carried out estimating time effect (post vs pre), group effect (HIIT vs MICT) and the interaction time x group. P value <0.05 will be considered as significant. Correlation between parameters will be analyzed using the Pearson Correlation Test or Spearman's Rank Correlation Test, depending on the nature of the conditional distribution and the shape of the relation.

Research Calendar

Provisional schedule

Beginning of inclusions: June 2015

Duration of the inclusion period: 1 year

Duration of participation of each patient: 7 months (4 weeks in rehabilitation centre)

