There are no plans to replace people who permanently stop the search. The data will be excluded from the statistical analysis. A temporary or permanent stop of the research will be automatically documented in the medical file.

Research Monitoring Committee

Research Monitoring Committee is composed of:

[name] (PU-PH, scientific manager)

[name] (Cardiologist, investigator)

[name] (PH, Scientific Officer)

[name] (Cardiologist, Scientific Officer)

[name] (PhD, Deputy Director of Clinique Saint Orens, project leader)

[name] (Teacher in Adapted [name] student, coordinator of the project)

The Research Monitoring Committee will meet 3 times: before the start of the research for the implementation visit, once 10 patients are included in the study, and at the end of the last end-of-study visit of the last patient. The Supervisory Committee ensures the smooth running of the research.

Ethical and regulatory compliance

Exams and methods used in this research are part of the routine care as defined by Law No. 2004-806 of 9 August 2004 (Article L1121-1, 2^o paragraph and Article R1121-3 of the Public Health Code). This study is a Clinical Routine Care Study

The instigator, the coordinator, and the investigators who drive and supervise the research undertake that this research is carried out in accordance with the law n° 2004-806 of August 9th, 2004, as well as in line with **Good Clinical Practice and the Declaration of Helsinki** (Ethical Principles for Medical Research Involving Humans, Tokyo 2004).

The research will be conducted in accordance with this protocol. Except in emergency situations requiring the implementation of specific therapeutic acts.

This research received the favourable opinion of the **Committee for the Protection of Persons** (ethical committee) (CPP) Sud-Ouest and Outremer II on May 6, 2015. This research is covered by the liability insurance of La Clinique Saint Orens.

The data recorded during this research are in accordance with the law n° 78-17 of January 6, 1978 relating to data, files and freedoms modified by the law 2004-801 of August 6, 2004. The Saint Orens Clinic will send a request for an opinion to the Advisory Committee on the Treatment of Information in the Field of Health Research (CCTIRS) and a request of authorization to the National Information Commissioner's Office / French Data Protection Authority (CNIL).

References

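### Night-time HFnu is compared between arms by what amounts to a change-score t-test; an ANCOVA on the D0 value already collected would usually be more precise

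*Combined protocol and SAP*

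**What the plan says.** The design is a "Prospective / randomized study in 2 parallel groups (1:1"). The main objective is to compare "exercise training programs (MICE vs HIIT) on the evolution of the spectral high frequency (HF) component of HRV". The Primary endpoint section defines the outcome as the evolution of night-time HFnu from D0 to W4, and the Sample Size section agrees: "The primary outcome measure is the change of High Frequency power in normalized units (HFnu) measure at night".

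The D0 value is in hand for every patient, since "24-h ECG monitoring will be performed at baseline and at the end of the stay". The follow-up table lists the Holter at both visits.

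The only between-arm analysis is in Statistical analyses: "repeated ANOVA analysis will be carried out estimating time effect (post vs pre), group effect (HIIT vs MICT) and the interaction time x group". A single threshold of P < 0.05 follows. The section does not say which of the three effects decides the trial, and no covariate adjustment appears anywhere.

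The sample size rests on a relative difference of about 11%, 90% power and these inputs: "With a mean value of the main criteria (HFnu %) of 31.5%, a standard deviation of 3" percent, with "risk set to 0.05 in bilateral hypothesis, 16 patient per group must be recruited". It does not say whether the SD describes a single reading or the change, and it gives no correlation between D0 and W4. The final stop rules add: "There are no plans to replace people who permanently stop the search. The data will be excluded from the statistical analysis".

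**The concern.** With two time points, the time x group interaction uses D0 only by subtracting it from W4, which fixes the regression slope of W4 on D0 at 1. In most settings the slope is below 1, so subtraction over-corrects and adds noise. ANCOVA estimates the slope instead. Under randomisation both methods target the same HIIT minus MICE difference, so the choice affects precision and not bias.

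Precision matters in a trial of 32 patients with no allowance for dropout, where patients who stop are neither replaced nor analysed.

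A smaller point is that three effects are listed and none is named as primary. The words evolution and change point to time x group. The group effect is also a valid 5% test of HIIT against MICE. It is a weak one, because averaging in the pre-training reading halves the targeted difference.

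**Working it through.** **Inputs from the Sample Size section.** Mean 31.5, relative difference 11%, so the difference is 0.11 x 31.5 = 3.465 HFnu points; SD 3; two-sided alpha 0.05; power 90%; 16 per arm.

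**Assumed, because the documents do not give it.** The D0-W4 correlation ρ: 0.3, 0.5 and 0.7. The SD of 3 is taken first as the SD of a reading and then as the SD of the change. D0 and W4 SDs are equal unless stated.

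**1. The plan's own figure.** The normal approximation gives n = 2 x [3 x (1.960 + 1.282) / 3.465]² = 15.75, so 16 per arm, with 90.4% power. This reproduces the stated number. The noncentral t gives 88.5% at 16 per arm and needs 17 for 90%. The noncentral t is used below for both methods.

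**2. Interaction and change-score test are the same.** On a simulated data set with 16 per arm, the time x group F and the squared change-score t were both 17.365.

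**3. Formulas.**
- Change-score SD = reading SD x √(2(1−ρ)), with 2n−2 degrees of freedom.
- ANCOVA residual SD = reading SD x √(1−ρ²), with 2n−3 degrees of freedom and variance multiplied by 1 + 1/(2n−4) for chance baseline imbalance (29/28 at n = 16; 25/24 at n = 14).
- If 3 is the SD of the change, reading SD = 3/√(2(1−ρ)).
- Variance ratio, ANCOVA to change score, at n = 16: (1+ρ)/2 x 29/28.

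Example with ρ = 0.3 and SD of a reading: change SD = 3√1.4 = 3.550; residual SD = 3√0.91 = 2.862; ratio = 0.65 x 29/28 = 0.67.

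**4. Results, interaction → ANCOVA.** The 14-per-arm column is an assumed number of completers.

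| SD 3 is of | ρ | Variance ratio | Power, 16 per arm | 95% CI half-width | n per arm for 90% | Power, 14 per arm |
|---|---|---|---|---|---|---|
| a reading | 0.3 | 0.67 | 76.2 → 90.2% | 2.56 → 2.11 | 24 → 16 | 70.1 → 85.5% |
| a reading | 0.5 | 0.78 | 88.5 → 94.8% | 2.17 → 1.91 | 17 → 14 | 83.7 → 91.3% |
| a reading | 0.7 | 0.88 | 98.3 → 99.1% | 1.68 → 1.58 | 11 → 10 | 96.7 → 98.1% |
| the change | 0.3 | 0.67 | 88.5 → 97.0% | 2.17 → 1.78 | 17 → 12 | 83.7 → 94.6% |
| the change | 0.5 | 0.78 | 88.5 → 94.8% | 2.17 → 1.91 | 17 → 14 | 83.7 → 91.3% |
| the change | 0.7 | 0.88 | 88.5 → 92.0% | 2.17 → 2.04 | 17 → 15 | 83.7 → 87.7% |

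The half-width is 18%, 12% and 6% narrower at the three correlations. Simulation with 200,000 trials per setting agrees with the ANCOVA powers to about 0.1 point.

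**5. Where 90% is reached at 16 per arm.** The interaction needs ρ of about 0.525 if 3 is the SD of a reading, and never reaches 90% if it is the SD of the change. With equal SDs, ANCOVA reaches it on both interpretations for ρ from 0.3 to 0.83.

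**6. Where the gain ends.** With equal SDs, break-even is ρ = 2 x 28/29 − 1 = 0.931. If the W4 SD is k times the D0 SD, the ratio is k²(1−ρ²)/(1+k²−2ρk) x 29/28. At ρ = 0.3, 0.5 and 0.7 this gives 0.81, 0.92 and 1.02 for k = 1.25, and 0.52, 0.59 and 0.65 for k = 0.8. If the slope is exactly 1 and the SD of the change is 3, the half-width goes from 2.17 to 2.21 and power from 88.5% to 87.3%.

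**7. Group effect.** The targeted difference is 3.465/2 = 1.73 and the SD is reading SD x √((1+ρ)/2). Power at ρ = 0.3, 0.5 and 0.7 is 50, 45 and 40% (SD of a reading) or 64, 45 and 26% (SD of the change).

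**8. Type I error.** In simulated null trials (SD 3 of a reading) the interaction rejected in 5.0%, ANCOVA in 5.0 to 5.1% and the group effect in 4.9 to 5.0%. A rule accepting either the group effect or the interaction would reject in 9.6 to 9.8%, but the plan contains no such rule.

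**The case against.** The planned test is valid, matches a change endpoint and, by the plan's own approximation, meets the 90% target. The step from 90.4% to 88.5% comes from using the exact t distribution and would arise for any two-sample comparison; ANOVA did not cause it. This stands, and the case for ANCOVA should rest on the paired comparisons in the table.

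The size of the gain depends on two things the documents do not give. The largest figure, 76 to 90%, needs both ρ = 0.3 and an SD of a reading. At ρ = 0.7 the gain is about 1 point (reading) or 3.5 points (change). This also stands. Uncertainty about ρ still favours ANCOVA, which estimates the slope where the change score assumes it is 1.

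The 0.3 to 0.83 range requires equal SDs. If the W4 SD is 1.25 times the D0 SD, ρ = 0.7 and the SD of the change is 3, ANCOVA power is 87.9% against 88.5%. This exception is real and small.

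ANCOVA does not cure attrition: at 14 per arm it too falls below 90% in two of the six rows. Excluding patients who stop is a separate issue.

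Finally, the follow-up table puts randomisation and the D0 Holter at the same visit, so a D0 reading might follow the first session. The Statistical analyses section treats D0 as the pre-training value, and a late reading would affect the change score as well, so this does not favour the ANOVA.

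**Conclusion.** The point holds as a matter of efficiency. The planned test is unbiased and keeps its 5% level. For assumed correlations of 0.3 to 0.7 with equal SDs, ANCOVA removes 33 to 12% of the variance of the between-arm estimate and adds 1 to 14 points of power with the same patients. The gain is negligible at ρ = 0.9, gone near 0.93, and can reverse slightly when the W4 SD is clearly larger than the D0 SD. The largest loss, at a slope of exactly 1, is about 1.2 points. The trade favours ANCOVA, and the change should be made, although the trial is not invalid without it. The plan should also name its deciding effect.

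**What to change.** Replace the between-arm sentence for the primary endpoint with wording such as: *The primary analysis is an ANCOVA of W4 night-time HFnu on arm, with D0 night-time HFnu as covariate. The adjusted HIIT minus MICE difference, its 95% CI and two-sided p-value are the sole basis for the primary conclusion.* Report the HFnu time effect, group effect and within-arm tests as descriptive.

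If the repeated-measures ANOVA is kept, add one clause naming the time x group interaction as the sole primary test.

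The cost is SAP wording and no new measurement. In the analysis it is one degree of freedom and a 29/28 variance penalty at 16 per arm.

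### The only analysis of the fitness, vagal tone and arrhythmia link is a correlation with no term for arm; if arms are pooled, treatment effects alone can produce a correlation

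*Combined protocol and SAP*

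**What the plan says.** Under Hypothesis, the combined protocol and SAP sets out two numbered expectations: "We therefore hypothesize that HIIT is superior to MICE for 1/ increasing parasympathetic activity measured by HRV, 2 / the cardiorespiratory fitness". It then adds a further one: "we also hypothesize that there is a link between improved physical capacity and vagal tone and decreased arrhythmias".

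Under Statistics, Statistical analyses, one sentence could serve that further hypothesis: "Correlation between parameters will be analyzed using the Pearson Correlation Test", with a Spearman rank version as the alternative. The choice between the two tests is made "depending on the nature of the conditional distribution and the shape of the relation", that is, on distributional grounds and not by arm. The sentence does not say which variables are paired, whether levels or changes are correlated, or whether the arms are pooled, separated or adjusted for.

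Arm is handled elsewhere in the same paragraph, for the comparison of the programmes: "repeated ANOVA analysis will be carried out estimating time effect (post vs pre), group effect (HIIT vs MICT) and the interaction time x group". A single threshold of P below 0.05 is given for all tests.

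**The concern.** A bivariate correlation cannot tell two situations apart. In one, patients who gain more fitness also gain more vagal tone. In the other, HIIT raises the average of both and the two gains are unrelated among patients who had the same training. In the second situation the pooled data form two clouds shifted along the diagonal, and the shift alone gives a non-zero correlation.

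The trial's own hypotheses predict the condition that causes this: an arm effect on HRV and an arm effect on fitness. The better HIIT works on both, the more likely a pooled test is to support the link whether or not it exists within arms. A difference between programmes could then be reported as a patient-level relation and read as support for a mechanism.

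**Working it through.** **Inputs from the documents.** Design of the study: two parallel arms, 1:1. Sample Size: "we hypothesise that HIIT mode will induce a ~11% change in HFnu compare to MICT training mode"; HFnu averaging 31.5 (per cent); SD 3; two-sided alpha 0.05; power 90%; 16 per group.

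**The plan's own figure first.** An 11% change on 31.5 is 0.11 × 31.5 = 3.465 points. The standardised effect is d1 = 3.465 / 3 = 1.155. By the normal approximation, n = 2 × (1.960 + 1.282)² / 1.155² = 15.8, so 16 per group, with power 90.4%. The stated size reproduces. A t-based calculation gives 16.8, so 17, which makes no difference to this point.

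**Assumptions.** The plan's SD of 3 is taken as the SD of the HFnu change, as its sample-size calculation implies. The documents give no effect size for fitness or arrhythmias, so the standardised arm effect on the second variable, d2, is varied from 0 to 1.5. Change scores are taken as normal, pooled over 32 patients, with zero correlation inside each arm.

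**Correlation created by arm alone.** With 1:1 allocation, the difference in means adds d²/4 to each variance and d1·d2/4 to the covariance, so

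r = (d1·d2/4) / √[(1 + d1²/4)(1 + d2²/4)].

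For d1 = d2 = 1.155: 1.155²/4 = 0.3335, and r = 0.3335 / 1.3335 = 0.25.

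**Rejection rates.** From 40,000 simulated trials per setting, 16 per arm, two-sided 0.05 (30 degrees of freedom pooled, 29 adjusted for arm):

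| d1 (HFnu) | d2 (second variable, assumed) | r from arm alone | Pooled Pearson | Pooled Spearman | Pearson adjusted for arm |
|---|---|---|---|---|---|
| 1.155 | 0 | 0.00 | 4.9% | 4.9% | 5.0% |
| 1.155 | 0.3 | 0.07 | 6.8% | 6.8% | 4.9% |
| 1.155 | 0.5 | 0.12 | 10.3% | 10.2% | 5.1% |
| 1.155 | 0.8 | 0.19 | 17.8% | 18.0% | 4.9% |
| 1.155 | 1.155 | 0.25 | 29.4% | 30.3% | 5.0% |
| 1.155 | 1.5 | 0.30 | 41.0% | 42.9% | 5.2% |
| 0.3 | 0.3 | 0.02 | 5.4% | 5.5% | 5.3% |
| 0.5 | 0.5 | 0.06 | 6.2% | 6.2% | 5.0% |
| 0.8 | 0.8 | 0.14 | 11.7% | 11.5% | 5.1% |

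Choosing Spearman does not protect the pooled test. A rank correlation adjusted for arm also stays near 5%.

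**Price of adjusting.** The smallest significant |r| moves from 0.349 (pooled, 30 degrees of freedom) to 0.355 (adjusted, 29). Testing each arm separately would need |r| above 0.497 with 14 degrees of freedom.

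**The case against.** Four points can be made for the plan.

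- **The plan does not say that the arms are pooled.** A reader might infer from the absence of an arm term that the plan has decided to ignore arm. The documents do not support that. They are silent, and the same paragraph analyses changes within groups, so per-arm correlations are not excluded. This stands, and the inflation above is therefore conditional on pooling. The silence still leaves the choice open until the data are seen, and the pooled test has the easier threshold (0.349 against 0.497).
- **A pooled correlation is not wrong in itself.** If HIIT raises vagal tone through fitness, the between-arm covariance is part of the link, and adjusting for arm removes it. This stands in part: the rates above are false positives only for an association within arms. But a pooled test cannot separate that pathway from two unrelated effects of HIIT. If fitness gain drives vagal tone, patients within an arm who gain more fitness should also gain more HFnu, and the adjusted test can detect that. This is a reason to show the pooled estimate with a clear label, not to rest the hypothesis on it.
- **The size rests on assumed effects.** This stands. The HFnu effect is the planning value, taken from the team's earlier study, which the Hypothesis section describes as single sessions in 18 patients. The effect on the second variable is given nowhere. If either effect is near zero, or both are 0.5 SD or less, there is little inflation.
- **The analysis is secondary in standing.** The link follows the two numbered hypotheses as an addition and does not appear among the objectives or the endpoints. This stands and limits the weight of the point. It is nevertheless a stated hypothesis, and the plan gives only one significance threshold.

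**Conclusion.** The point holds in conditional form. The plan's only analysis of a stated hypothesis has no term for arm and leaves pooling open. If changes are pooled and HIIT shifts both variables, as the trial expects for HRV and fitness, the test can favour a link that is absent among patients in the same arm. At the planned HFnu effect, the false-positive rate for a within-arm link runs from 5% (no second effect) to 29% (equal effects) and to 41% at an assumed 1.5 SD. It is 5 to 6% when both effects are 0.3 or both 0.5 SD. These figures assume normal change scores. They do not cover arrhythmia counts, which two of the three natural pairs involve.

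A reader might also infer that the planned analysis misstates an association within patients. The documents do not support that wording: the follow-up table has two assessments, so each patient contributes one change score per variable, and no within-patient association can be estimated by this plan or by the fix. The relevant comparison is among patients in the same arm. The primary endpoint, the sample size and the HIIT against MICE comparison are unaffected.

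**What to change.** Rewrite the correlation sentence in Statistical analyses to say that:

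- the link is examined on change scores from D0 to Week 4, for three named pairs: VO2peak with HFnu, HFnu with arrhythmia count, and VO2peak with arrhythmia count;
- the test of the link is the partial correlation adjusted for arm, Pearson or rank, with the existing rule on distribution and shape deciding between them;
- pooled and per-arm correlations are shown descriptively, and the pooled one is labelled as including the difference between arms.

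This needs a few lines of text, no further patients or measurements, and one degree of freedom.
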